9 SUBJECT MANAGEMENT

9.1 Subject Follow-up

9.1.1. In home assessments.

Participants will complete an at-home symptom questionnaire by REDcap on each day of follow-up through day 28, including in-home assessments of temperature and O2 saturation. These assessments will be reviewed daily by a clinical research coordinator, and patients will be telephoned by a physician if they report an elevated temperature, diminished O2 sat (<94%), or signs/symptoms of respiratory or cardiopulmonary distress (e.g. shortness of breath, dyspnea on exertion). On each day through day 28, patients will also be instructed to collect an anterior nare swab in a pre-labeled container and to store these specimens in a refrigerator at 2°C to 8°C, and to bring these in to their next scheduled appointment. Prior to the optional follow up visits at months 4, 7 and 10, participants will complete an at-home symptom questionnaire and will be asked to collect a stool specimen to bring to their next scheduled appointment.

9.1.2. Follow-up in-clinic assessments.

[figure not shown]
Participants will be seen at follow-up visits at Day 1±1, 3±1, 5±1, 7±1, 10±1, 14±1, 21±1, and 28±1. At each visit, a subjective medical history will be performed, including assessments for use of any concomitant medications. Vital signs will be obtained (temperature, blood pressure, pulse rate per minute, breath rate per minute and oxygen saturation), and oropharyngeal and anterior nare swabs will be collected. Participants will also submit at-home collected anterior nare swab specimens for evaluation. Clinical laboratory measurements will be performed at days 5±1 and 14±1 to assess for safety, with additional clinical laboratory assessments performed as needed for clinical follow-up and/or patient management. Additionally, ~25 mL peripheral blood will be collected from study participants at enrollment and at Days 5±1, 14±1, and 28±1 for processing and cryopreservation into a specimen biobank. Safety and tolerability of Lambda will be assessed by adverse event (AE) monitoring, vital signs assessment and clinical laboratory tests. Patients will reach the end of study at day 28±1 of follow-up. Optional long-term follow up visits will be scheduled 4, 7, and 10 months post-enrollment. The window of ±3 weeks is allowed for these long term follow up visits.

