10 WITHDRAWAL OF SUBJECTS AND MANAGEMENT OF PROTOCOL VIOLATIONS

10.1 Withdrawal of subjects from the study

Participants will be followed until they reach 28 days post-randomization, with optional follow-up for up to 10 months. Study participants will be prematurely withdrawn from the study for: 1) inability to be located for >7 consecutive days, 2) withdrawal of informed consent, 3) inability to comply with the study schedule and procedures (e.g., missing 3 of the first 6 in-person visits), 4) at the discretion of the site investigator if the study is not in the best interest of the participant, 5) subject judged by the site investigator to be at significant risk of failing to comply with the study protocol as to cause them harm or seriously interfere with the validity of study results. If a subject is withdrawn for reasons # 1 or 2, we will be unable to perform any additional study procedures. If a subject is withdrawn for reasons # 3-5, plans to obtain appropriate follow-up tests outside of the study will be individualized for each subject depending on the health status of the subject at the time of withdrawal and the willingness of the participant and his or her parent/guardian to proceed with additional testing.

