### **2.4 Secondary efficacy analyses**

Time to resolution of all symptoms will be defined as the time from randomization until the first study day in which no symptoms are reported. The distribution of time to resolution of symptoms will be estimated using the Kaplan-Meier method, and Kaplan-Meier curves will be presented for each treatment arm. Time to symptom resolution at the end of the study period along with 95% confidence intervals will be presented for each treatment arm. The hazard ratio for resolution of symptoms will be estimated, along with its 95% confidence intervals, from a Cox proportional hazards model adjusted for age and sex.

We will model SARS-CoV-2 viral load in oropharyngeal tests over time using a generalized mixed effects linear regression model with a random effect for study participant to account for correlation within a participant. Viral load with cycle threshold (Ct) values above the limit of detection will be calculated by substituting a Ct value of 42 into the equation  $10^{(Ct - 42) * 0.23}$  to derive viral load from Ct. A logarithmic transformation on viral load will be fit to treatment arm, time, armXtime, and adjusted for age and sex to account for therandomization stratification variables. The armXtime interaction term will allow us to assess whether the trajectory of viral load differs by treatment arm. Time will be defined as days from randomization and, depending on model fit, will either be modeled continuously or with a flexible approach allowing a non-linear trajectory for the change in viral load over time. Model fit will be assessed based on visual inspection of the residuals. Alternative transformations or generalized linear models with a link function besides the identity link will be considered if the model does not fit the data well.

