Area under the curve (AUC) will be defined by a single participant's logarithmic base 10 viral load from oropharyngeal tests collected on days 0, 1, 3, 5, 7, 10, and 14. AUC will be calculated by the trapezoidal rule, using exact times of collection of each OP swab. Multiple imputation using chained equations will be used to impute missing viral load data prior to AUC calculation. Five data sets will be imputed, and imputed values will be calculated using non-missing viral load on each of the 7 sample collection days, treatment arm, age, sex, and whether or not a participant was hospitalized. A pooled linear regression model will be fit to log-transformed AUC as a function of treatment, age, and sex using the 5 imputed data sets. Difference in AUC by treatment arm and corresponding 95% confidence intervals will be reported using Rubin's Rules. The difference in AUC by treatment arm will also be done after refitting the model without participants who were hospitalized to assess sensitivity of results.

The incidence of hospitalizations and emergency department visits will be estimated for each arm, with 95% confidence intervals.

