## 2.5 Exploratory efficacy analyses

An alternative definition of the secondary endpoint of symptom resolution will be considered in an exploratory analysis. We will evaluate time to sustained symptom resolution, defined as time from randomization until the first day in which no symptoms are reported and are not reported for the duration of the study. The analysis of time to sustained symptom resolution will follow the methods described for the secondary endpoint evaluation symptom resolution in the previous section. Time to symptom resolution based on symptom subsets (i.e. respiratory, systemic) will be similarly analyzed, additionally excluding participants who did not report symptoms from the specified subset at screening.

Time to disease progression will be defined as the time from randomization until the first day of a two point or more increase in either cough or shortness of breath persisting for at least 48 hours or an increase to a score of 4 or 5, or first day of admission to the emergency department, hospitalization, or death. Analysis and reporting of results will be done following methods detailed for time to symptom resolution.

Freedom from SARS-CoV-2 infection by oropharyngeal and nasal swabs at Day 5, 7, 10, and 14 will be modeled using a multivariable logistic regression model adjusted for age and sex. The odds ratio will be presented along with its 95% confidence interval.

Similar approaches to those used for evaluating SARS-CoV-2 viral load in oropharyngeal tests over time and AUC will be used to evaluate viral load in nasal tests.

Correlation between virology and symptomology will be characterized by evaluating the relationship between CT values obtained from the oropharyngeal tests and each symptom through two main approaches. For symptoms graded on an ordinal scale, we will calculate a Spearman correlation and assess significance with a Z-test. For variables that capture presence of a symptom, differences in the median CT values by presence or absence of the symptom will be presented and assessed via a Wilcoxon rank sum test.

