## 3 HANDLING OF MISSING AND CENSORED DATA

All efforts will be made to minimize instances of missing data. However, we expect some missing data will occur. Our analyses will assume data are missing at random. For the primary endpoint of time to shedding cessation, any participant who drops out prior to having two consecutive negative tests will be censored at their last positive test. Participants who have no post-randomization test results available or a single test result that is negative will be censored at day 1. Similarly, participants will be right censored for the time to symptom resolution or progression at the time when their last symptom questionnaire is completed. Participants who are asymptomatic at screening and never report symptoms thereafter will be considered to have met symptom resolution at study Day 1. For other missing data, we will use multiple imputation-based analyses. This approach will be applied to any analysis involving endpoints or key

variables where any missing data occurs in order to adhere to the ITT principle. Sensitivity to assumptions regarding missingness will be addressed through sensitivity analyses.

If more than 5% of participants do not have the time of shedding cessation observed (i.e. they are right-censored), we will perform a sensitivity analysis to evaluate the robustness of our findings to missing data assumptions. In the sensitivity analysis, among those missing timing of shedding cessation, we will assume varying proportions (e.g. 25%, 50%) of participants in each arm who would have ceased shedding by Day 28. The proportions will differ by arm so we can evaluate whether our findings stand if it were true that people who dropped out stopped shedding earlier in the placebo arm vs the active arm.

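### If an unresolved participant dies, or is admitted and stops answering the symptom questionnaire, SAP 3 censors symptom resolution at the last questionnaire, and that censoring is informative

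*SAP*

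**What the plan says.** SAP 2.4 defines time to resolution of all symptoms as "the time from randomization until the first study day in which no symptoms are reported". It is analysed by Kaplan-Meier, with a hazard ratio "from a Cox proportional hazards model adjusted for age and sex". Neither SAP 2.4 nor Protocol 12.4 says what happens to this endpoint on admission or death, and neither names a competing-event method. The exploratory resolution endpoints in SAP 2.5 (sustained resolution and the symptom subsets) follow the same methods.

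SAP 3 supplies the censoring rule, "participants will be right censored for the time to symptom resolution or progression at the time when their last symptom questionnaire is completed", and the general assumption, "Our analyses will assume data are missing at random".

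Symptoms come from one home instrument: "Participants will complete an at-home symptom questionnaire by REDcap on each day of follow-up through day 28" (Protocol 9.1.1). The protocol does not stop the questionnaire at admission, and it does not say how symptoms are recorded in hospital.

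Elsewhere the SAP does take account of admission. The progression endpoint counts it as an event: "or first day of admission to the emergency department, hospitalization, or death" (SAP 2.5). For viral load AUC, the imputation model includes "whether or not a participant was hospitalized", and the model is refitted without hospitalised participants (SAP 2.4).

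**The concern.** Kaplan-Meier and Cox give a valid answer under right censoring only if a censored participant has the same later chance of the event as comparable participants still under observation. A participant who has died cannot resolve. One who is admitted with unresolved symptoms and stops answering has been selected for getting worse. If these participants leave the risk set when the questionnaires end, the estimated resolution curve is too high.

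Protocol 3.2 puts duration of symptoms and hospitalisations or ED visits in the same secondary objective, so a difference in admissions between arms is part of what the trial looks for. If Lambda prevents admissions, the rule takes part of that benefit out of the symptom result. If Lambda causes them, the rule hides part of the harm.

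**Working it through.** The documents state no figure for this point, so there is none to reproduce. The check has two parts: what the text implies, and an illustration of size.

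**1. What the text implies**

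| Unresolved participant | Treatment under SAP 2.4 and SAP 3 |
|---|---|
| Dies | Questionnaires end, so censored at the last one |
| Admitted, never answers again | Censored at the last one |
| Admitted, answers in hospital or after discharge | Not censored at admission |
| Had a symptom-free day before admission | Already counted as resolved |

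Only the top two rows are a problem.

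**2. Inputs for the illustration**

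- From the documents: 60 per arm, 1:1 allocation, follow-up to Day 28, Kaplan-Meier and Cox.
- Assumed, because the documents do not give them: exponential resolution with median 9 days, admission between days 2 and 10, and admission rates of 2% to 10% per arm.
- Worst case: every admitted participant stops answering and none recovers by Day 28.
- The Cox models are unadjusted, with 20,000 simulated participants per arm. A hazard ratio (HR) above 1 means faster resolution on Lambda.

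**3. Kaplan-Meier**

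Resolution by Day 28 among those not admitted is 1 − 2^(−28/9) = 0.884.

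- At 10% admitted, the proportion resolved with the admitted kept as unresolved is 0.90 × 0.884 = 0.796. The simulated estimate under the SAP rule is 0.877, about 8 points higher.
- At 3% admitted, it is 0.97 × 0.884 = 0.858, against about 0.884 under the SAP rule, between 2 and 3 points higher.

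**4. Hazard ratio, no other treatment effect**

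| Admitted, control vs Lambda | SAP rule | Kept unresolved to Day 28 | Difference |
|---|---|---|---|
| 3% vs 3% | 0.998 | 1.003 | about 0 |
| 5% vs 2% | 1.029 | 1.082 | 0.053 |
| 10% vs 3% | 1.047 | 1.183 | 0.136 |
| 3% vs 10% | 0.965 | 0.858 | −0.107 |

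These runs treat everyone marked for admission as never resolving (setup A). If a symptom-free day before admission counts as resolution, as SAP 2.4 would have it, fewer participants are affected. At 10% vs 3% the HR is then 1.00 under the SAP rule and 1.09 when kept, a difference of 0.09 (setup B). Hence the range 0.09 to 0.14.

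With an HR of 1.3 among those not admitted (setup A), the rule gives 1.349 against 1.467 at 10% vs 3%, and 1.221 against 1.037 at 3% vs 10%. At 10% in both arms it gives 1.300 against 1.240, so equal admission rates leave the HR unchanged only when there is no other effect.

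**5. Scale**

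About 0.86 × 120 = 103 resolutions give SE(log HR) ≈ √(4/103) = 0.197, or about 0.20.

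- 10% vs 3%, setup A: ln(1.183/1.047) = 0.122, about 0.6 SE.
- 10% vs 3%, setup B: ln(1.09/1.00) = 0.086, about 0.4 SE.
- 5% vs 2%: ln(1.082/1.029) = 0.050, about 0.25 SE.

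In patients, 10% vs 3% of 60 is about 6 vs 2, and 5% vs 2% is about 3 vs 1.

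**6. Relaxing the worst case (10% vs 3%, no other effect)**

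The complete-data HR is the one obtained if every admitted participant's recovery were recorded.

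| Setup | Stop answering | Admitted who recover by Day 28 | Complete data | SAP rule | Kept unresolved |
|---|---|---|---|---|---|
| A | all | none | 1.19 | 1.05 | 1.19 |
| A | all | about 45% | 1.13 | 1.05 | 1.20 |
| A | all | about 70% | 1.07 | 1.03 | 1.18 |
| A | half | about 45% | 1.11 | 1.07 | 1.14 |
| B | all | none | 1.09 | 1.00 | 1.09 |
| B | all | about 45% | 1.03 | 0.99 | 1.08 |
| B | all | about 70% | 1.01 | 0.99 | 1.08 |

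In every row the complete-data value lies between the other two, or equals the kept value. At 70% recovery in setup A the SAP rule is low by 1.07 − 1.03 = 0.04, and keeping everyone unresolved is high by 1.18 − 1.07 = 0.11.

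**The case against.** A reader might infer that the SAP censors hospitalised participants at admission. It does not say so. SAP 3 never mentions hospitalisation in this rule, Protocol 9.1.1 runs the questionnaire to Day 28, and admission is not a listed reason for withdrawal in Protocol 10.1 (although missed clinic visits can lead to withdrawal). The problem arises only when reporting stops for good. That part of the objection stands and makes the point conditional, except for death, where reporting must stop.

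A reader might also extend the point to progression, because the quoted sentence names it. That would be wrong: an admission or death is an event there.

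The effect on admissions is not lost to the trial, since ED visits and hospitalisations are a separate secondary endpoint. This limits the damage, but it does not make the symptom hazard ratio correct.

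SAP 3 promises sensitivity analyses for missing-data assumptions, and SAP 2.7 extends sensitivity analyses to other key endpoints. Neither names this problem. The only worked-out analysis of departures from missing at random concerns shedding, and multiple imputation is reserved for missing data other than these censored endpoints.

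The strongest objection is that counting non-responders as unresolved replaces one untested assumption with another. Step 6 bears this out: if many admitted participants recover unrecorded, that analysis overshoots, sometimes by more than the current rule errs. It is therefore not safely conservative, and it needs the current rule reported beside it.

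**Conclusion.** The point holds for time to symptom resolution and the exploratory resolution endpoints that follow its methods. An unresolved participant who dies, or who is admitted and stops reporting, is censored informatively. Resolution is then overstated, and a difference in admissions is understated in the hazard ratio, to the benefit of the arm with more admissions.

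The size cannot be derived from the documents. The HR shifts of 0.09 to 0.14 (10% vs 3%) and about 0.05 (5% vs 2%) rest on assumed admission rates and on the worst case of permanent non-response and no recovery by Day 28. They are upper bounds for those rates, not estimates of the bias. All are below one standard error of the log hazard ratio. Because the endpoint is secondary, this is a cheap improvement of modest severity and no threat to the primary result.

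**What to change.** Add to SAP 3, for the symptom-resolution endpoints only: a participant who dies before resolution, or who is hospitalised before resolution and has no later questionnaire, stays in the risk set as unresolved to Day 28. Any later questionnaire is used when available. Report the present last-questionnaire censoring as a sensitivity analysis. The two results bracket the answer provided that admitted non-responders recover no faster than participants still reporting. Leave the progression endpoint as it is.

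The cost is a sentence or two in the SAP and one extra model fit, with no new patients or data and no change to the primary endpoint. The downside should be stated in the SAP: if many admitted non-responders recover before Day 28 without a record, the main analysis overshoots in favour of the arm with fewer admissions.

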3.2. Secondary objectives

- To evaluate the efficacy of subcutaneous injection of a single dose of 180 mcg of Peginterferon Lambda-1a compared with placebo, in reducing the duration of symptoms, hospitalizations, or ED visits in patients with uncomplicated COVID-19 disease.
- To evaluate the safety and tolerability of subcutaneous injection of a single dose of 180 mcg of Peginterferon Lambda-1a compared with placebo.

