5.2. Secondary efficacy endpoints

- SARS-CoV-2 RNA levels during follow-up
- SARS-CoV-2 viral load area under the curve
- Time to alleviation of all symptoms (fever, chills, cough, nasal congestion, muscle pains), defined as the time from initiation of treatment until all symptoms are rated as absent or mild in symptomatic patients
- Incidence of emergency department visits or hospitalizations within 28 days of initiation of treatment

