6.2 Inclusion Criteria

Patients must fulfill all of the following inclusion criteria to be eligible for the study:

1. Age \geq 18 years and \leq 75 years at the time of the assessment
2. Able and willing to understand the study, adhere to all study procedures, and provide written informed consent
3. Diagnosis of COVID-19 disease:
 - a. If symptomatic, presence of mild to moderate symptoms without signs of respiratory distress, with FDA-cleared molecular diagnostic assay positive for SARS-CoV-2 within 72 hours from swab to the time of commencing informed consent:
 - b. If asymptomatic, initial diagnosis of SARS-CoV-2 infection with positive FDA-cleared molecular diagnostic assay obtained no more than 72 hours from initial swab to the time of commencing informed consent

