12 STATISTICAL METHODS AND CONSIDERATIONS

12.1 Analysis population

We will evaluate the intention-to-treat (ITT) population. The intent-to-treat (ITT) population will include all randomized patients. Patients will be analyzed according to their assigned treatment arm. All efficacy analyses will be completed in the ITT population. The per-protocol (PP) population will include all randomized patients who completed follow-up and adhered to study procedures. All efficacy analyses will be also be completed in the PP population as supportive evidence for the primary efficacy analysis. The safety population will include all patients who receive study treatment. Patients will be analyzed according to actual treatment received. All safety analyses will be completed in the safety population.

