12.3 Analysis of primary endpoint

Time until shedding cessation will be compared between the two treatment arms using a two-sided Cox proportional hazards model adjusted for age and sex. The test will be performed at the alpha = 0.05 level of significance. The hazard ratio for shedding cessation will be estimated, along with its 95% confidence interval, from a Cox proportional hazards model. If the proportional hazards assumption is not met, we will consider an extended Cox model that relaxes the proportional hazards assumption.

The distribution of shedding cessation will be estimated using the Kaplan-Meier method, and Kaplan-Meier curves will be presented for each treatment arm. Time to shedding cessation at the end of the study period along with 95% confidence intervals will be presented for each treatment arm.

In a subgroup analyses, the time until shedding cessation analyses will be performed separately in the symptomatic and asymptomatic participants.

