12.4 Analysis of secondary endpoints

SARS-CoV2 Log₁₀ viral loads at follow-up timepoints will be compared between groups using the Wilcoxon rank-sum test and/or generalized estimating equations with robust standard errors. The area-under-the-curve (AUC) SARS-CoV2 viral RNA levels during follow-up will be estimated using the linear trapezoidal method, and mean AUC levels compared between groups using the Wilcoxon rank-sum test.

The distribution of cessation of symptoms will be estimated using the Kaplan-Meier method, and Kaplan-Meier curves will be presented for each treatment arm. Time to cessation of symptoms at the end of the study period along with 95% confidence intervals will be presented for each treatment arm. The hazard ratio for cessation of symptoms will be estimated, along with its 95% confidence intervals, from a Cox proportional hazards model. Time to cessation of symptoms will be estimated in the subgroup of patients who are symptomatic at baseline.

The incidence of hospitalizations and emergency department visits will be compared between groups using negative binomial regression models, which will account for differing follow-up times through an offset term.

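### Time to symptom resolution has a different population, event and start time in the Protocol and the SAP, and the SAP brings in never-symptomatic enrollees as Day 1 events

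*SAP*

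**What the plan says.** **Protocol.** The secondary objective (3.2) concerns Lambda's efficacy "in reducing the duration of symptoms, hospitalizations, or ED visits in patients with uncomplicated COVID-19 disease". Section 5.2 names fever, chills, cough, nasal congestion and muscle pains, and gives the endpoint as "defined as the time from initiation of treatment until all symptoms are rated as absent or mild in symptomatic patients". Section 12.4 describes Kaplan-Meier and Cox analyses and ends: "Time to cessation of symptoms will be estimated in the subgroup of patients who are symptomatic at baseline". Section 12.1 carries a general sentence: "All efficacy analyses will be completed in the ITT population".

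Asymptomatic infection is an explicit route into the trial (6.2: "If asymptomatic, initial diagnosis of SARS-CoV-2 infection with positive FDA-cleared molecular diagnostic assay"). Section 12.3 expects such patients, since "the time until shedding cessation analyses will be performed separately in the symptomatic and asymptomatic participants". The symptomatic route in 6.2 requires "presence of mild to moderate symptoms without signs of respiratory distress".

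**SAP.** Section 2.4 runs the clock from randomization to the first day on which the participant reports no symptoms. It gives neither a symptom list nor a population. Section 2.1 places all efficacy analyses in the ITT population. Section 3 then states: "Participants who are asymptomatic at screening and never report symptoms thereafter will be considered to have met symptom resolution at study Day 1". For the exploratory respiratory and systemic subsets, section 2.5 excludes people who lacked those symptoms at screening. Section 2.7 plans a symptomatic-only subgroup for the primary endpoint.

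**The concern.** A person who never has symptoms has no symptom duration for treatment to shorten. Counting that person as resolved on Day 1 adds an event in either arm, whatever the drug does. If Lambda does shorten symptoms, such events dilute the estimated HR and shorten the reported times in both arms.

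The more basic problem is that the two documents describe different endpoints. A patient left with only a mild cough has met the Protocol event but not the SAP event. An asymptomatic enrollee is outside the Protocol population but is an event in the SAP analysis. Without a statement of which version is main, the choice could be made after the data are seen.

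**Working it through.** **Side by side.**

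| Element | Protocol 5.2 and 12.4 | SAP 2.1, 2.4 and 3 |
|---|---|---|
| Population | Symptomatic patients; symptomatic at baseline | ITT; never-symptomatic enrollees included through the Day 1 rule |
| Event | All symptoms absent or mild | No symptoms reported |
| Symptom list | Five named | None; exploratory endpoints in SAP 1.4 name others, such as sore throat, headache and fatigue |
| Time origin | Start of treatment | Randomization |

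That the SAP analyses all randomised patients is an inference. Section 2.4 does not say so, but 2.1 does for efficacy in general, and the Day 1 rule has a purpose only if these people are in the analysis.

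**No plan figure to reproduce.** Neither document gives a power or sample size for this endpoint. What follows is an illustration of size.

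**Inputs.** From the SAP: 60 per arm (1.1), follow-up to day 28 (1.2), and HR 2.03, borrowed from the shedding calculation (4.2). Assumed: exponential symptom durations, a 9-day placebo median, 10% drop-out spread evenly over days 1 to 28, and the asymptomatic share *f*.

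**Mechanism.** The chance that a symptomatic patient resolves on Day 1 is 1 − exp(−ln 2/9) = 0.0741 on placebo and 1 − exp(−2.03 × ln 2/9) = 0.1447 on Lambda, a ratio of 1.95. With *f* = 10% scored as Day 1 events:

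- Placebo: 0.10 + 0.90 × 0.0741 = 0.1667
- Lambda: 0.10 + 0.90 × 0.1447 = 0.2303
- Ratio: 1.38

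At *f* = 20% the ratio is (0.20 + 0.80 × 0.1447)/(0.20 + 0.80 × 0.0741) = 1.22. After Day 1 only symptomatic people remain and the full effect returns, so the Cox HR lies between the two.

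**Simulation.** Durations rounded up to whole days; unadjusted Cox model with Efron ties; Wald test at 0.05; 10,000 trials per setting, with both analyses run on the same trials. True HR 2.03:

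| *f* | HR, all randomised | Power, all randomised | Power, symptomatic only | Loss (points) |
|---|---|---|---|---|
| 5% | 1.96 | 93.4% | 94.5% | 1.1 |
| 10% | 1.89 | 90.3% | 93.1% | 2.8 |
| 20% | 1.76 | 82.7% | 90.5% | 7.8 |
| 30% | 1.63 | 71.0% | 86.3% | 15.3 |

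The symptomatic-only HR was 2.03 to 2.05 throughout.

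**Sensitivity.** At a true HR of 1.5, the all-randomised HR is 1.45 at 10% and 1.38 at 20%, with losses of 4.2 and 8.3 points. With a placebo median of 6 or 14 days (HR 2.03), the loss is 2.9 or 3.8 points at 10%, and 6.4 or 9.6 at 20%.

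**True null.** The HR is 1.00, with 4.8% rejections at 10% asymptomatic and 5.5% at 20%.

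**Does the Protocol event avoid immediate events?** Not necessarily, because 6.2 admits patients with mild symptoms. Take 54 per arm with any symptom (60 less 10% asymptomatic) and keep the absent-or-mild event. If 10%, 20% or 40% of them have only mild symptoms at baseline (assumed), the HR is 1.90, 1.76 or 1.51. Power is 87.5%, 78.6% or 52.2%, against 90.9%, 87.5% or 75.8% when those patients are left out.

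**The case against.** **The ITT principle calls for everyone.** Protocol 12.1 does put all efficacy analyses in the ITT population, and the last sentence of 12.4, read alone, could describe an added subgroup analysis. That reading of 12.4 is fair. But 5.2 is the endpoint definition and contains the restriction itself. Selecting on a characteristic recorded before randomisation, and analysing by assigned arm, keeps the randomised comparison.

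**SAP 2.7 already covers it.** Its symptomatic-only subgroup is named for the primary endpoint. The closing sentence extends sensitivity and effect-modification analyses to other key endpoints, without naming this subgroup or this endpoint. At best it gives a supportive analysis.

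**The SAP is the later, governing text.** Its revision history says it was updated to match the Protocol and declares no change to this endpoint.

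**The size is unknown and the effect conservative.** This stands. The asymptomatic share, the duration distribution and the effect on symptoms are all assumptions. At 10% or less the loss is small. The weight of the point rests on the contradiction, not on the power table.

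**A stronger reading to avoid.** A reader might infer that the SAP version understates a real effect compared with the Protocol version. The documents do not support that. The dilution is shown only for the Day 1 rule with the event held fixed. The Protocol's absent-or-mild event can create immediate events of its own, of similar or larger size, depending on how many enrollees have only mild symptoms. Neither document gives that number.

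**Conclusion.** The contradiction is established from the text: population, event threshold, symptom list and time origin all differ. The SAP is also inconsistent within itself, since 2.5 excludes from the symptom subsets the kind of participant that section 3 counts as an event in the parent endpoint.

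For a given event definition, the Day 1 rule attenuates a real effect: to an HR of about 1.9 at 10% asymptomatic and 1.75 at 20%, from a true 2.03, with power losses of about 3 and 8 points. These figures depend on the assumed exponential durations, 9-day placebo median and HR. There is no bias under a true null and no effect on the primary endpoint. Which document's version is the more diluted overall cannot be settled from what they give. The change should be made because this is a secondary efficacy endpoint with two competing definitions, but it does not threaten the trial's main conclusion.

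**What to change.** 1. In SAP 2.4 and 2.5, make the main analysis of time to symptom resolution and of sustained resolution the randomised participants who are symptomatic at baseline, analysed by assigned arm. Keep the all-randomised Day 1 version as a labelled sensitivity analysis.
2. Reconcile the event threshold, symptom list and time origin between Protocol 5.2 and SAP 2.4, and state which definition is main.
3. If the absent-or-mild event is kept, state how patients who already meet it at baseline are handled. Excluding them is one option, provided baseline severity is recorded for each symptom. SAP 2.5 indicates that some symptoms are graded and others recorded only as present or absent, so this needs checking.
4. State how people asymptomatic at screening who later report symptoms are handled. The Day 1 rule covers only those who never do, and under the wording of SAP 2.4 the others could count as resolved before their symptoms begin.
5. Report the number of asymptomatic enrollees by arm.

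**Cost.** SAP wording, plus a change to Protocol 5.2 if the SAP event is kept. Screening symptom status is already used in SAP 2.5 and 3. The main analysis of this secondary endpoint loses patients asymptomatic at baseline, including those who later become symptomatic. It would also lose those with only mild symptoms at baseline if the option in item 3 is taken.
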